4.3.2.6.5 Coefficient of Variability (CV) CGM BG

$$CV \text{ of Daily CGM BG} = \frac{SD \text{ of Daily CGM BG}}{Mean \text{ of Daily CGM BG}}$$

4.3.2.7 Performance of the Investigational Infusion Set

4.3.2.7.1 Daily Insulin Infusion Set Survival Rate

Infusion set failure is defined as an episode of unexplained hyperglycemia that did not respond to a correction bolus, hyperglycemia associated with elevated serum ketone measurement in the absence of evidence of intercurrent illness, evidence of infusion site infection, or non-resolvable insulin infusion pump occlusion alarm. These conditions indicate failure of the system at the level of the subcutaneously indwelling infusion cannula.

Infusion sets can also fail to provide insulin as a result of other system performance issues, such as failure of the insertion attempt to pierce the skin, accidental removal of the set by inadvertent application of tension to the tubing (e.g. “tubing caught on a doorknob”), or failure of the adhesive to secure the cannula housing to the skin for the full duration of study.

The daily infusion set survival rate is calculated by the # of non-fail infusion sets on that day divided by the total # of infusion sets inserted. Survival curves will be generated for both “infusion set failure” episodes and all failures combined (“infusion set failure” combined with “other system performance issues” as defined above).

The day will be normalized to the day of the insertion where first day is set to Day 0.

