7 DISCONTINUATION AND WITHDRAWAL

7.1 DISCONTINUATION OF STUDY INTERVENTION

7.1.1 INFUSION SET CHANGE-OUT/EARLY DROPOUT

Independent of the time point for infusion set removal/change out, study staff is to follow the SOP for Infusion Set Removal and the reason for change-out is to be documented in the applicable source document and CRF.

We anticipate several commercial and/or investigational CSII catheters to fail prior to the fourth glucose clamp experiment on day 7. Participants will be instructed to contact the research investigator by telephone (24/7) to confirm the diagnosis of a failed CSII catheter. If the CSII catheter does not fail before day 7, the investigational/commercial CSII set will be removed upon completion of the clamp experiment on Visit 4A/Visit 4B. The site and cannula will be photographed, and the cannula inspected under a microscope.

The following are objective criteria that define a CSII catheter/infusion set failure:

1. The occurrence hyperglycemia (glucose >250 mg/dL) not responsive to a pump bolus dose where response to the bolus is defined as a fall of at least 50 mg/dL in blood glucose within one hour.
2. The occurrence of hyperglycemia (glucose >250 mg/dL) after prolonged fasting (e.g. overnight or more than 5 hours following a meal), not associated with acute intercurrent illness, but with a concurrent ketone level ≥ 0.6 mmol/L.
3. Signs of inflammation/infection at the infusion site including pain, erythema or induration >10 mm in diameter.
4. Occurrence of an insulin pump occlusion alarm signal.

In the case that any of the above occurs during home-use, the participant is asked to call the 24/7 helpline and confirm catheter failure with the study staff. The study participant will insert a new commercial CSII catheter (as used routinely by this patient) into the subcutaneous tissue at an alternate location and connect it to the insulin pump for routine glycemic management. The failed CSII catheter will be left in place. The participant is asked to measure erythema around the catheter and photograph the site. The study participant will return to the study site as soon as practicable so the research staff can remove and observe the failed CSII catheter. Study staff is to follow the SOP for catheter removal.

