4.4.4 Efficacy analyses

4.4.4.1 Analyses of Primary Endpoints

Our primary endpoint is the failure rate of infusion set. A descriptive summary of infusion set failures will be provided. The summary will be reported for each period.

The $AUC_{0-300(GIR)}$ on day of insertion (day 0) and days 3, 5, 7 in periods 1 and 2 will be calculated using the trapezoidal rule as described in section 4.3.2.1.

The nature log of AUC: $\ln(AUC_{0-300(GIR)})$ will then be calculated.

A mixed-effects (repeated-measures) linear model with *treatment* and *period* as fixed effects and participant as a random effect will then be fit to this data. Estimates of the slopes by treatment will be generated as contrasts based on the least squares means. The contrast is: the difference in slopes (control minus Achilles) of $AUC_{0-300(GIR)}$ versus day, computed from the least squares means of $AUC_{0-300(GIR)}$ at each study day within each of the 2 periods.

Treatment comparisons and confidence bounds on the difference in slopes will be presented.

The primary analysis will be conducted on the ITT population using all available data within the mixed model repeated measures framework. Missing an $AUC_{0-300(GIR)}$ assessment will be assumed missing at random (MAR). However, a sensitivity analysis will be done to check the extent to which the missing data could have made a difference in the conclusions of the analysis.

Additionally, the same analyses will be repeated on the baseline adjusted AUC_{0-300} and ITT population.

Population	ITT and PP (ITT is the primary , PP is the sensitivity)
------------	---

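### The SAP narrows the protocol's definition of infusion-set failure without declaring it, so some protocol-defined failures can drop out of the survival comparison

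*SAP*

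**What the plan says.** Protocol 7.1.1 introduces its list with "The following are objective criteria that define a CSII catheter/infusion set failure". The first two items are hyperglycemia that does not respond to a bolus, and fasting hyperglycemia with raised ketones. The third is "Signs of inflammation/infection at the infusion site including pain, erythema or induration >10 mm in diameter". The fourth is "Occurrence of an insulin pump occlusion alarm signal". Infection is not required for the third, and the fourth does not depend on whether the alarm can be cleared.

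SAP 4.3.2.7.1 keeps both hyperglycemia items in substance. The rest of its definition is "evidence of infusion site infection, or non-resolvable insulin infusion pump occlusion alarm". It then adds a second category: "Infusion sets can also fail to provide insulin as a result of other system performance issues, such as", followed by failed insertion, accidental removal and loss of adhesion as examples. Survival curves are planned for failure "episodes and all failures combined", the second curve being the sum of the two categories. The daily survival rate is the number "of non-fail infusion sets on that day divided by the total # of infusion sets inserted".

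SAP 4.2.6 treats a study set as removed for the period once the participant switches to another set. SAP 4.4.4.2.1 compares set survival with a discrete life table and a log-rank test. SAP 2.5 records the early termination and its consequences, and no change to the failure definition.

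**The concern.** Two documents that govern the same endpoint classify the same set differently. A set that meets the protocol's third or fourth criterion may not be a failure in the SAP. Set survival is a named secondary endpoint with a formal test, and both documents tie the safety objective to set failure (protocol 3.3, SAP 2.3).

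The omission need not be neutral between devices. Protocol 2.2.1 reports less inflammation around the investigational cannula in swine, alongside less kinking and a larger insulin surface-to-volume ratio. If site inflammation differs between the two sets in patients, leaving it out of the failure variable could hide an advantage or a harm as well as shift the overall level.

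**Working it through.** **Step 1. Compare the definitions.**

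| Item | Protocol 7.1.1 | SAP 4.3.2.7.1, failure | SAP 4.3.2.7.1, other issues |
|---|---|---|---|
| Hyperglycemia, no response to bolus | yes | yes | – |
| Hyperglycemia with ketones | yes | yes | – |
| Site infection | yes | yes | – |
| Inflammation >10 mm without infection | yes | not named | not named |
| Occlusion alarm that cannot be resolved | yes | yes | – |
| Occlusion alarm that is resolved | yes | no | not named |
| Failed insertion, accidental removal, adhesion loss | not listed | no | yes |

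Infection cannot safely be read to include inflammation, because SAP 4.3.3.1.3 names the two separately.

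**Step 2. Trace one set.** Take a set with erythema above 10 mm, no infection, still delivering insulin, and changed out between the day 3 and day 5 clamps.

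- Protocol 7.1.1: a failure under the third criterion, replaced after staff confirm it.
- SAP 4.2.6: removed for that period, with no statement on event or censoring.
- SAP 4.3.2.7.1, first category: not infection, so not a failure.
- SAP 4.3.2.7.1, second category: described as failure to deliver insulin, which this set did not show.
- Daily rate: the denominator is every set inserted. A set not classed as failed can stay in the numerator on days 5 and 7.

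Time to device failure (SAP 4.3.2.7.2) has the same gap.

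**Step 3. Illustrate the size.** Neither document gives a figure for this discrepancy, so there is none to reproduce. Protocol 2.2.3 gives failure modes from a 7-day steel-versus-Teflon crossover trial: hyperglycemia 30%, pain 13%, accidental removal 10%, erythema or induration >10 mm 10%, adhesion loss 5%, infection 4%. Assume these rates apply here.

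- Protocol criteria: 30 + 10 + 4 = 44%. With removal for pain under the third criterion: 44 + 13 = 57%.
- SAP infusion set failure: 30 + 4 = 34%.
- SAP combined curve: 34 + 10 + 5 = 49%.
- Protocol failures in neither SAP curve: 10 points, or 10 + 13 = 23 points with pain.
- Share of protocol failures omitted: 10/44 = 23%, or 23/57 = 40% with pain.
- Seven-day survival without pain: 100 − 44 = 56% by the protocol, 100 − 34 = 66% by the SAP's main curve.

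The combined curve exceeds 44% only because it adds 15 points of events outside the protocol's list. It still lacks the 10 points for erythema or induration.

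The listed causes sum to 30 + 13 + 10 + 10 + 5 + 4 = 72%, against a stated 7-day failure rate of 64%, so the sums are approximate. No rate is given for resolved alarms, and their effect cannot be computed.

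**Step 4. Scale to the data in hand.** Assume 7 sets per device, one for each completer. One reclassified set moves a survival rate by 1/7 = 14.3 points. At a 10% rate the expected number is 7 × 0.10 = 0.7 sets per device, and the chance of at least one is 1 − 0.9^7 = 52%.

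**The case against.** Several arguments limit the point.

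- **The second SAP category is open.** Its examples follow a phrase that marks them as examples, so a reader cannot say outright that inflammation removals are counted nowhere. This stands in part. The category is still confined to sets that do not deliver insulin, which does not naturally describe removal for a local reaction.
- **Nothing states that such a set survives.** A reader might infer that it is definitely scored as surviving. The documents do not say so: SAP 4.2.6 is silent on event, censored or surviving. The supportable criticism is that this is unspecified, and that the rate formula allows it.
- **A cleared alarm need not end wear.** Protocol 4.1.3 has the user check for clogs and leaks and change the set if in doubt. Protocol 7.1.1 has staff confirm the failure, and protocol 6.1.1.8 ends the treatment phase at change-out. A set that alarms, clears and stays in use is not obviously misclassified by the SAP. The concern here is the set changed out after an alarm that cleared.
- **The 23-point figure needs every pain removal to count.** The third protocol criterion does not clearly make pain alone a failure, so 10 points is the safer figure. Protocol 9.4.1 also expects fewer early removals here, because staff insert and secure the sets.
- **The events are not lost.** Infection or meaningful inflammation is counted with hours since insertion (SAP 4.3.3.1.3), and alarms are counted daily (SAP 4.3.2.7.3 and 4.3.2.7.4). This is correct, but those counts are descriptive and do not enter the life table or the log-rank test.

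SAP 4.4.4.1 says "Our primary endpoint is the failure rate of infusion set", and a reader might infer that the primary analysis is affected. The documents do not support that. The protocol synopsis, protocol 9.4.2 and SAP 4.3.2.3 base the primary analysis on the glucose infusion rate AUC, and SAP 4.4.4.1 itself gives failures only a descriptive summary. That sentence is a separate conflict and does not raise the weight of this one.

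**Conclusion.** The definitions differ on two of four criteria, and SAP 2.5 does not declare the change. Followed as written, the SAP can leave protocol-defined failures out of both survival curves and the log-rank comparison, because the status of a removed but unclassified set is not stated.

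The illustrative size is about 10 percentage points, and up to 23 if removal for pain counts. This rests on transferring the cited trial's failure modes to this trial and on adding causes that do not sum exactly to its stated total. Resolved alarms are not included.

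This should be fixed, but it is not critical. It affects a secondary endpoint in a trial stopped after 7 completers. It still matters because SAP 2.5 says that every defined analysis will be run, and with so few sets a single reclassification is visible.

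**What to change.** Reconcile protocol 7.1.1 and SAP 4.3.2.7.1 for endpoint classification.

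1. Use the protocol's failure criteria for the survival endpoint and report the narrower SAP version as a sensitivity curve. Alternatively, keep the narrower definition, and declare and justify it in SAP 2.5.
2. State whether a study set removed before day 7 for any other reason is an event or censored, both in the life table and in time to device failure. Make SAP 4.2.6 and the daily rate formula agree with that.
3. Say how removal for pain alone and an alarm that clears with the set kept in use are classified.

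The cost is SAP wording and one extra curve. Protocol 7.1.1 already requires the reason for change-out on the CRF, so no new data are needed. This concerns how sets are counted in the analysis, not which clinical change-out rule is right.

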4.3.2.7.2 Time (h) to Device Failure

Time to device failure = date/time when device fails – date/time of Day 0 (as defined in section 4.3.2.7.1) . It will then be transformed to hours.

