Secondary Endpoints 4:	
 • Proportion of investigational CSII sets that did not fail on each day of use. • Mean difference across treatments in time to device failure • Mean difference across treatment in incidence of pump bolus occlusion alarms • Mean difference across treatment in incidence of pump basal occlusion alarms

Safety Objectives:	To assess Achilles infusion set safety and tolerability from DOI through day 7 for each treatment
Safety Endpoints:	
 • The occurrence hyperglycemia (glucose >250 mg/dL) not responsive to a pump bolus dose where response to the bolus is defined as a fall of at least 50 mg/dL in blood glucose within one hour, • The occurrence of hyperglycemia (glucose >250 mg/dL) after prolonged fasting (e.g. overnight or more than 5 hours following a meal), not associated with acute intercurrent illness, but with a concurrent ketone level ≥ 0.6 mmol/L. • Localized infection or inflammation of greater than 1.0 cm in diameter at the infusion site • Occurrence of an insulin pump occlusion alarm signal • Cannula dislodgement from subcutaneous space, • Cannula malfunction (inability to pierce skin, bending, kinking, fluid leakage or other malfunction that might impact insulin infusion) • Mean visual analog scores (VAS) scores (0-100 mm) from Day of insertion through Day 7 of use • Mean difference of VAS scores (0-100mm) of CSII investigational sets and CSII control sets • Descriptive statistics of per subject term, severity, adverse device effects, and frequency of adverse events for each treatment • Descriptive statistics of per subject incidence of unanticipated adverse device effects
Study Population:	
Up to 30 adult participants, with the goal of having approximately 24 completers, may be enrolled, ages 18–70, diagnosed with Type 1 diabetes mellitus (T1DM) who have ≥ 6 months experience using rapid-acting insulin analog delivered via Medtronic MiniMed insulin pump and infusion sets. Only Medtronic pump models 530 and higher may be used.
 
Study participants will be drawn from existing T1DM patient populations meeting the study eligibility at each study center and from referral practices.

Phase:	Phase 1b
Description of Sites /Facilities Enrolling Participants:	This study will be conducted at no more than 5 centers in the United States. Each site will be qualified to conduct insulin treatment studies per a standardized euglycemic clamp protocol.

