Recent data (discussed below) indicate that this 65% failure rate at seven days likely overstates the actual failure rate likely to occur when using the Silhouette infusion set for up to seven days. In the Patel study, out of eighty possible seven-day wear periods in the twenty study participants studied, infusion set failure was attributed to non-correctable hyperglycemia in only 30% of the wear periods (regardless of infusion set type). Other modes of failure were noted to account for the remaining failure events (infusion site erythema, infection, infusion site pain, accidental removal, adhesive failure). Thus, one-half of the infusion sets that did not perform through seven days were removed for reasons other than hyperglycemia.

15% of Teflon sets (Medtronic QuickSet) used in the Patel study were removed due to kinking upon insertion, which was diagnosed within the first few hours of use by the development of uncorrectable hyperglycemia or a pump occlusion alarm. This suggests that only about 23% of sets in the study (30% of steel infusion sets and 15% of Teflon infusion sets) failed due to uncorrectable hyperglycemia occurring after the first few hours of wear time. No cases of ketosis were reported in the study, meaning that study participants were able to detect and attempt to correct hyperglycemia before the

development of more serious metabolic derangement. It should be noted that the paper was published in 2014, well before the introduction of more sophisticated and accurate CGM systems that are now in use.

Recent data presented in February 2020 in Madrid by Medtronic indicated a 49% survival rate at seven days for the QuickSet (as compared to 32% in the Patel study), again suggesting that the expected failure rate in the control arm of the proposed study is not likely to be as high as that observed in the Patel study.

Therefore, the risk associated with infusion failure in the control arm with extended use for up to seven days is not considered to be unreasonable or detrimental to the study participants. The risk will be appropriately managed with a combination of modern real time CGM, close supervision by study site personnel, and appropriate education of study participants.

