considered failed, a new fresh commercial insulin infusion set inserted and another bolus is given. Patients will stay at the CRU until they have finished their meal and their BG has dropped as assessed by two blood glucose meter measurements in the range of 90 – 200 mg/dL separated by at least 30 minutes.

The study participant will be provided with a meal at the conclusion of the clamp visit. Insulin lispro will be infused through the study investigational or commercial CSII catheter using the participant's typical basal/bolus pattern of delivery during home care between study visits. Study personnel will call the participant the same evening to ensure the participant's wellbeing.

6.1.1.6 VISITS 2, 3, AND 4

Participants arrive the prior evening for stabilization and procedures explained above in section "Visit 1" are repeated (except insertion of CSII catheters). If CGM failed, a new CGM will be inserted by trained study staff.

If the CSII catheter does not fail before day 7, the investigational/commercial CSII set will be removed upon completion of the clamp experiment on Visit 4A/Visit 4B. The site and cannula will be photographed, and the cannula inspected under a microscope. A fresh CSII catheter (as routinely used by the participant) will be inserted at a different site, the pump connected, and routine glycemic management resumed. The change-out will be documented in the appropriate source documents and CRF.

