using an aseptic technique), we anticipate having lower failure rates related to early catheter removal. We therefore assume a 40-50% failure rate to be a reasonable estimate of total anticipated failures and have added 6 additional participants for an anticipated total sample size of n=30. (Statistical analyses were performed using Systat version 13.)

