4.2 Data Handling Conventions

4.2.1 Missing Data

- Any blank value will be treated as missing (unknown)
- Blank values will be left as blank in the data listings.
- Missing data will not be imputed unless specified

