4.4.2 General Consideration of Descriptive Summary

The following rules will be used, unless specific described, for any descriptive summary.

1. Descriptive summary will be by treatment and by period
2. For continuous variables: mean, SD, median, minimum and maximum will be reported. Two decimal points will be used unless specified.
3. For category variables: count, percentage, and the total used as a denominator will be reported. One decimal point will be used unless specified.

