4.4.4.2.4 Other Efficacy Endpoints

For other efficacy endpoints listed in section 4.3.2, descriptive summary will be presented.

Population	ITT
------------	-----

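### Time to device failure has no censoring rule, so its planned mean covers failed sets only and can understate or even reverse a real difference between sets

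*SAP*

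**What the plan says.** The Protocol synopsis lists, under the fourth secondary objective, "Mean difference across treatments in time to device failure". SAP 4.3.2.7.2 builds the variable: "Time to device failure = date/time when device fails", less the Day 0 date and time, converted to hours. It says nothing about a set that does not fail.

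The SAP gives the variable no analysis section of its own, so the catch-all in 4.4.4.2.4 applies: "For other efficacy endpoints listed in section 4.3.2, descriptive summary will be presented". SAP 4.4.2 says what that summary contains for a continuous variable: "mean, SD, median, minimum and maximum will be reported", by treatment and by period. On absent values, SAP 4.2.1 states: "Missing data will not be imputed unless specified". Nothing is specified for this variable.

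Follow-up has a planned end. Protocol 6.1.1.6 (repeated in 7.1.1) says: "If the CSII catheter does not fail before day 7, the investigational/commercial CSII set will be removed upon completion of the clamp experiment", meaning the Visit 4 clamp, which the schedule of activities places at 168 ± 3 h after insertion. Protocol 9.4.1 expects many sets to get that far: "We therefore assume a 40-50% failure rate to be a reasonable estimate of total anticipated failures".

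Separately, SAP 4.3.2.7.1 plans a daily survival rate with all inserted sets as denominator, and survival curves for two failure definitions: cannula-level failures alone, and those combined with other system problems such as accidental removal or adhesive loss. SAP 4.4.4.2.1 compares the sets by a discrete life table and log-rank test. Protocol 9.4.9 adds exploratory Kaplan-Meier curves and a Cox frailty model.

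**The concern.** A set that lasts the full week is the best result this device can give, and it is the one result for which the variable has no value. With no censoring time and no imputation, the reported mean is an average over failures. It describes when failing sets fail and carries nothing about how often sets fail, which is the main question for an extended-wear set.

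Two sets that differ greatly in how many survive can then show nearly the same mean. A set with few failures, all early, can show a shorter mean than a set that fails often through the week. A reader who takes the secondary endpoint at its name would read that as a shorter-lasting device.

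**Working it through.** The documents give no expected value, event count or power for this variable, so there is no stated figure to reproduce. The check compares what the definition yields with a summary that counts every set.

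**Inputs from the documents.** Failure rate 40–50% (Protocol 9.4.1). Failure above 15% by day 1 and above 25% by day 3 (Protocol 2.3.3, Table 4). Recent data with a "49% survival rate at seven days for the QuickSet" (Protocol 2.3.3). Observation ends at about 168 h. The remaining survival values below are assumptions.

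**1. Sets without a value.** 1 − 0.50 = 50% to 1 − 0.40 = 60%. Per set type this is 12 to 14.4 of the planned 24, or 3.5 to 4.2 of 7. A within-participant difference needs failure in both periods. If failures are independent (assumed), that is 0.40² = 16% to 0.50² = 25% of participants: 3.8 to 6 of 24, or 1.1 to 1.8 of 7. If failures cluster completely within participants, it is 40–50%.

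**2. How the two summaries relate.** Let F be the proportion failed by 168 h and m the mean time among failed sets. The restricted mean is R = F × m + (1 − F) × 168. The plan as written reports m. The term (1 − F) × 168 is what it leaves out.

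**3. Constant hazard.** With 7-day survival S, λ = −ln(S)/7 per day, m = 1/λ − 7S/(1 − S) and R = (1 − S)/λ.
- S = 0.49: λ = 0.1019; m = 9.813 − 6.725 = 3.09 days = 74.1 h; R = 0.51/0.1019 = 5.00 days = 120.1 h.
- S = 0.80 (assumed better set): λ = 0.03188; m = 31.37 − 28.00 = 3.37 days = 80.9 h; R = 0.20/0.03188 = 6.27 days = 150.6 h.
- Difference: 80.9 − 74.1 = 6.8 h among failed sets, against 150.6 − 120.1 = 30.5 h counting all sets. The sign is right, but most of the advantage disappears.

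**4. Early failures in the better set.** Failures are spread evenly within each interval. Control survival is 85/75/62/49% at days 1/3/5/7 (days 1 and 3 at the Table 4 bounds, day 7 from the 49% figure, day 5 assumed). The better set is assumed at 90/90/87.5/85%.
- Control: 0.15 × 0.5 + 0.10 × 2 + 0.13 × 4 + 0.13 × 6 = 1.575 days; m = 1.575/0.51 = 3.09 days = 74.1 h; R = 1.575 + 0.49 × 7 = 5.005 days = 120.1 h.
- Better set: 0.10 × 0.5 + 0.025 × 4 + 0.025 × 6 = 0.30 days; m = 0.30/0.15 = 2.00 days = 48.0 h; R = 0.30 + 0.85 × 7 = 6.25 days = 150.0 h.
- The failed-only mean puts the worse set ahead by 74.1 − 48.0 = 26.1 h. The restricted mean puts the better set ahead by 150.0 − 120.1 = 29.9 h.

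**5. The curves the Protocol quotes.** Protocol 2.2.3 gives survival for steel sets of 87/68/53/32% at days 3/5/6/7. For Teflon it gives 77/59/46/33% on the same days, after a 15% initial failure rate, taken here as day 1. The same method gives m = 111.0 and 90.1 h (difference 20.9 h) and R = 129.2 and 115.8 h (difference 13.4 h). The order holds, but here the failed-only mean overstates the difference. The direction of the error depends on when failures occur.

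**The case against.** The strongest case against this point has four parts.

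*No sentence excludes intact sets.* That is correct. The omission follows from the definition together with the general rule against imputation. A reader might infer a deliberate decision to drop day-7 survivors, and the documents do not support that. They are silent, but followed as written they leave those sets without a value and offer no other reading.

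*The SAP does not test this mean.* Also correct. The comparison wording is the Protocol's. The SAP plans a description only, with no test, interval or decision rule. The variable is still a named secondary endpoint, and a descriptive mean can mislead.

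*Survival is handled elsewhere.* This carries real weight. The daily survival rate, the survival curves and the life table with log-rank test all count intact sets. SAP 4.3.3.3 also summarises hours of device exposure without restriction to failed sets. Exposure is no substitute, because Protocol 7.1.1 leaves a failed set in place until the site removes it. A reader might infer that the comparison of device survival as a whole is unsound; these analyses show that it is not. None of them, however, is named as the analysis of this endpoint, and none alters the mean reported beside them.

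*The reversal is a chosen scenario.* It is. A reader might infer that this endpoint will favour the worse set. That needs the better set's few failures to come early, and the documents give no such pattern for Achilles. The Protocol expects its cannula to resist kinking, which is the early failure mode it describes. Reversal is absent under constant hazard and in the quoted steel and Teflon curves.

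**Conclusion.** The point stands as a defect in one descriptive secondary endpoint. As written, the summary conditions on failure and omits 50–60% of sets at the Protocol's planning rate. That rate is a pooled assumption built partly on a participant-level figure, so the share in either treatment may differ.

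The failed-only mean can shrink a real advantage (6.8 h instead of 30.5 h under constant hazard) and can reverse the order when the better set fails seldom but early (26.1 h the wrong way against 29.9 h the right way). These sizes rest on the assumed curves shown. What does not depend on them is that the reported mean carries no information on the proportion surviving.

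The parallel survival analyses limit the consequence. The early stop after the 7th completer sharpens it in one respect: with 40–50% of 7 sets failing, 2.8 to 3.5 sets per treatment would supply the mean, and one early failure could dominate it.

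**What to change.** Amend SAP 4.3.2.7.2 before the tables are produced:

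- Define a time and a status for every inserted set. A set removed intact at the planned day 7 visit (about 168 h), or removed earlier for a reason not counted as failure, is censored at removal.
- Apply this under each of the two failure definitions in 4.3.2.7.1. Accidental removal, for example, is an event under the combined definition and a censoring under the narrower one.
- Report by treatment the numbers failed and censored, and the restricted mean time to 168 h from the survival curve, in place of the raw mean of failed sets. A survival median is a poor substitute: at 50–60% survival it would generally not be reached by day 7.
- State that the restricted mean is the SAP's version of the Protocol's mean-difference endpoint. With about 7 completers, label any paired difference and its confidence interval as descriptive only.

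The cost is a paragraph of SAP wording and a modest amount of programming; the paired interval, if wanted, takes somewhat more care than the two curves. No new data are needed, because removal times and reasons for change-out are already recorded (SAP 4.3.3.3, Protocol 7.1.1).
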